### 3.7 Handling of Missing Data

Section 3.5 of this protocol defines the data sets that will be collected from patients. Any missing information in this regard would be considered as incomplete data and this will meet an exclusion criterion and thereby a participant would be totally excluded from the study even if all other parameters are present.

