## 1 Background

Refractive errors (myopia, hyperopia and astigmatism) are quite prevalent worldwide, they constitute the most common cause of visual impairment with myopia in particular being progressively increasing in its prevalence so that it is predicted that by 2050 nearly half of the world population will be myopic. Management modalities include correction with glasses, contact lenses, laser vision correction, intracorneal implants and intraocular refractive procedures such as phakic intraocular lens (PIOL) implantation which involves the use of implantable collamer lens (ICL) in many cases. PIOLs are being extensively used since they preserve the integrity of the cornea and thereby attaining higher quality of vision compared with conventional kerato-refractive procedures. Furthermore; they allow broader range of refractive errors to be corrected. The Staar V4c EVO visian ICL (Staar surgical Inc, Lake Forest, CA, USA) has demonstrated effectiveness and an excellent safety profile with more than one million ICL implants had already been performed globally. However, complications such as raised intraocular pressure (IOP), cataract and pupillary block do happen. The ICL implantation procedure typically utilizes viscoelastics to facilitate introduction and positioning of the implant. Viscoelastics should be removed thoroughly at the conclusion of the procedure, and failure to do so may induce early postoperative IOP rise. It is logical to assume that viscoelastics use during surgery increases operation cost and time due to the extra steps involving the injection and removal of the substance. Increased manipulation during ICL implantation surgery and irrigation required to ensure adequate removal of viscoelastics may encourage cataract formation as well. Few studies investigated the safety and efficacy of ICL implantation without the use of viscoelastics, where they implemented balanced salt solution (BSS) instead as a novel technique. In the present study we retrospectively investigated the safety and efficacy of modifying ICL implantation technique by using cohesive OVD only without using dispersive OVDs.

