### 3.3 Study Population

All refractive surgery candidates attending the above hospital for the purpose of phakic introcular lens implantation were included in the study. However, the initial group allocation occurred before the commencement of the study on the basis of surgeon and patient preference, thereby, randomization was on convenient basis.

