### **Inclusion Criteria**

Refractive surgery candidates

Aged from 18-55 years

Phakic intraocular lens implantation was performed (ICL type)

Committing to at least one preoperative visit for baseline assessment and multiple postoperative visits (at least 2 visits within a year) for follow-up assessment.

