### **Exclusion Criteria**

Patients with incomplete data and no commitment to follow up visits

Presence of the following ocular conditions preoperatively: unstable refraction, severe ocular surface disease, cataract, glaucoma, corneal pathology such as Fuch's dystrophy or corneal scarring, uncontrolled intraocular inflammation, macular scarring or any other retinal issue that may adversely affect vision after surgery.

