## **3.5 Study Interventions / Procedures**

After enrolment, the record of each participant is examined meticulously for completeness of preoperative and postoperative data pertaining to study including:

Patient age and gender, date of the procedure and its operative notes including laterality and surgical steps.

preoperative and postoperative assessments such as uncorrected and best corrected visual acuity, refractive error quantification both objectively utilizing an autorefractometer autorefractor Nidek ARK 1 (Nidek Inc, Gamagori, Japan) and subjectively as manifest refraction, clinical slit-lamp examination notes, intraocular pressure with air puff tonometers, AC depth assessment by Pentacam Scheimpflug (Oculus Optikgeräte GmbH Inc., Wetzlar, Germany), specular microscopy study of corneal endothelial cells (endothelial cell density (ECD), coefficient of variation (CV) and hexagonality) using Topcon SP-1p Specular Microscope (Topcon Corporation, Tokyo, Japan),

Typically, there is a preoperative visit and multiple postoperative visits extending over the period of 1-2 years after the procedure.

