## 2- Reduced OVD group

In this group of patients, the ICL was implanted with the use of cohesive OVD only.

There is one primary outcome of interest which is the unaided visual acuity after the surgery, and several secondary outcomes including postoperative intraocular pressure, corneal specular microscopy parameters (ECD, CV and hexagonality), and the observed adverse events that can happen during the operation or postoperatively.

Data will then be stored electronically in a sheet format to enable for later statistical analysis.

Data collection was started at the conduct of the study in March 2024, and it is expected to be completed 3-4 months later.

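### Two whole-study exclusion rules, for any missing Section 3.5 item and for fewer than two postoperative visits, have no exemption for adverse events, so complications on record in excluded patients are dropped

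*Combined protocol and SAP*

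**What the plan says.** Two rules act independently.

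- **Completeness.** Section 3.7 treats any missing part of the Section 3.5 data set as meeting an exclusion criterion, and says that "a participant would be totally excluded from the study even if all other parameters are present". Section 3.5 covers demographics, "date of the procedure and its operative notes including laterality and surgical steps", and a battery of eye examinations before and after surgery. It does not say which examination is required at which visit; it says only that records typically hold "multiple postoperative visits extending over the period of 1-2 years after the procedure".
- **Follow-up.** The Inclusion Criteria ask for a baseline visit and "multiple postoperative visits (at least 2 visits within a year) for follow-up assessment". Section 3.3.1.1 makes every inclusion criterion mandatory, so failing this one alone makes a patient ineligible.

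The Exclusion Criteria also list "Patients with incomplete data and no commitment to follow up visits". The joining word *and* could mean that both conditions are needed, but Section 3.7 and Section 3.3.1.1 with the Inclusion Criteria already make each sufficient alone.

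The aim in Section 2 asks whether the reduced-OVD technique is safe. Section 3.6 lists among the secondary outcomes "the observed adverse events that can happen during the operation or postoperatively". No section defines a separate safety set, exempts adverse events from either rule, or plans to report exclusions by group and reason.

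**The concern.** An intraoperative event needs no postoperative visit to be known. On incomplete removal of viscoelastic, Section 1 warns that "failure to do so may induce early postoperative IOP rise"; such a rise can be on record before a second visit takes place. Yet a patient with either event is removed from every analysis if, for example, anterior chamber depth is missing. That item is in the Section 3.5 data set but is not among the outcomes named in Section 3.6.

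Return visits and the completeness of postoperative records are determined after surgery. Complication rates computed after both rules are therefore conditional on events that follow the operation and may be related to how it went. At stake are the count of complications, the absolute rates, possibly the comparison between groups, and precision. Without a table of exclusions, a reader could not tell which of these was affected.

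**Working it through.** The plan states no sample size, power, event rate or missing-data rate, so there is no figure of its own to reproduce. The textual result (both rules are sufficient alone, neither exempts adverse events) follows from the passages set out above. The numbers below show only how the rules behave. **Every input is an assumption.**

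**Absolute rate.** Let p be the true event rate, a the share of patients with an event who are retained, and b the share retained among those without. Then

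observed rate = p·a / [p·a + (1 − p)·b].

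With p = 5%:

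| a / b | Calculation | Observed |
|---|---|---|
| 70% / 70% | 0.0350 / (0.0350 + 0.6650) | 5.0% |
| 60% / 80% | 0.0300 / (0.0300 + 0.7600) | 3.8% |
| 80% / 60% | 0.0400 / (0.0400 + 0.5700) | 6.6% |

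The rate is biased only if a and b differ, and it can move either way.

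**Comparison, same pattern in both groups.** Take true rates of 10% and 5%, ratio 2.00.

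- With 60%/80% the 10% becomes 0.060/0.780 = 7.69%, and the ratio is 7.69/3.80 = 2.03.
- With 80%/60% it becomes 0.080/0.620 = 12.90%, and the ratio is 12.90/6.56 = 1.97.

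The comparison is almost untouched.

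**Comparison, different patterns, both groups truly 5%.**

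- 70%/70% in one group and 60%/80% in the other gives 5.00/3.80 = 1.32.
- 80%/60% against 60%/80% gives 6.56/3.80 = 1.73.

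**Events lost.** Of 5 recorded events, 5 × (1 − a) are dropped: 1 at a = 80%, 2 at a = 60%. This loss occurs even when a = b and the rate is unbiased.

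**Precision.** I group Section 3.5 into 3 once-only blocks (age and gender, procedure date, operative notes) and 7 examination blocks (visual acuity, autorefraction, manifest refraction, slit lamp, IOP, anterior chamber depth, specular microscopy). With one preoperative and one postoperative time point that is 3 + 7 × 2 = 17 blocks. If every examination is required at two postoperative visits it is 3 + 7 × 3 = 24. If each block is missing independently with probability m, the retained share is (1 − m)^k, and confidence intervals widen by the factor (retained share)^(−1/2).

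| m | Retained, 17 blocks | Retained, 24 blocks | Retained if gaps wholly cluster |
|---|---|---|---|
| 1% | 84% | 79% | 99% |
| 2% | 71% | 62% | 98% |
| 5% | 42% | 29% | 95% |

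At m = 5% the width factor is 0.418^(−1/2) ≈ 1.5 for 17 blocks and 0.292^(−1/2) ≈ 1.85 for 24. If gaps fall in the same records it is 0.95^(−1/2) ≈ 1.03, almost no loss. None of these is an upper limit, because the number of required items is itself not defined.

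**The case against.** The strongest reply is that complete records are a declared eligibility rule in a retrospective convenience sample, and that the harm shown is possible rather than demonstrated. Much of this stands. Section 3.5 leaves open which items are needed at which visit, so the completeness rule could remove almost no one or a large share. Reading the inclusion criterion as visits attended is also an interpretation, since the text speaks of *committing* to them; in a records study it is the natural one.

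A reader might go further and infer that the rules bias the comparison between the two techniques, perhaps by hiding complications of one of them. The documents do not support that. A retention pattern shared by both groups barely moves the ratio, and the 1.73 above needs opposite patterns in the two groups, for which no section suggests a mechanism. Section 3.3 says that "the initial group allocation occurred before the commencement of the study on the basis of surgeon and patient preference". This means that equal retention cannot be assumed; it does not make unequal retention likely.

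What the reply does not answer is that the plan states a rule, and that following it discards recorded complications in excluded patients whatever the retention pattern. The statement in Section 3.3 that all candidates were included does not help, because the eligibility criteria and Section 3.7 narrow it.

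**Conclusion.** The point holds as a reading of the text: either rule alone removes a patient from the whole study, neither spares adverse events, and exclusions are not planned to be reported by group. Recorded events in excluded patients are lost in every case. Absolute complication rates are biased if retention differs by event status. The between-group comparison is materially distorted mainly if that pattern also differs between groups, which is neither shown nor ruled out.

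How many patients are affected, and the size and direction of any bias, cannot be learned from the documents. The ranges (3.8% to 6.6% for a true 5%; confidence intervals from about 1.0 to 1.85 times as wide) rest wholly on assumed rates, retention and item counts. I am confident of the textual defect and make no claim about the actual effect on results. This is a cheap improvement that should be made.

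**What to change.** 1. In Section 3.7, replace whole-study exclusion with exclusion only from analyses that need the missing item. Each between-group comparison uses patients with that outcome recorded; each pre/post comparison in Section 4.2 uses patients with both values.
2. Keep the two-visit rule for visual acuity, IOP and specular microscopy. Section 3.6 fixes no time point for the primary outcome, so dropping the rule there could let a single early acuity reading stand for it. For adverse events, lift both the two-visit rule and the completeness rule.
3. Count intraoperative events over all operated patients who meet the preoperative criteria and whose notes allow group assignment and event ascertainment. Count postoperative events over patients assessed in time windows fixed before the groups are compared. State how many were not seen in each window, so that short follow-up is not counted as freedom from late events.
4. Tabulate exclusions and missing data by group and reason, and keep the complete-record set as a sensitivity analysis.

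The cost is revised wording in the Inclusion Criteria, the Exclusion Criteria and Section 3.7, denominators that differ by outcome and window, and late windows that may hold few patients. Section 3.4 already has all records screened. Section 3.6 limits collection to records that meet the inclusion criteria, while Section 4.2 places the completeness check after collection. Re-extraction should therefore be needed mainly for patients who failed the two-visit criterion.

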## 4 Statistical Considerations

Biostatisticians had been consulted regarding the statistical analysis of data from this study.

### 4.1 Sample size and statistical power

This study involves a convenient non-probability sample based on the availability of patients records in the respective center for enrolment and analysis.

### 4.2 Statistical methods

After collection of data from patients records and its subjection to thorough analysis for incompleteness and exclusion criteria, these data will be stored electronically in sheet formats for later analysis. All statistical test and subsequent analyses will be performed using SPSS version 26 (IBM statistical software). Data will be classified into categorical and numerical. Categorical variables were described using frequencies and percentages and were analysed using Chi-squared test. Numerical variables, described as mean  $\pm$  standard deviation, will be subjected to tests of normality to determine the appropriate statistical tests for inter- and intra-group comparisons. Unpaired t test or Mann-Whitney test was used to compare the two groups (traditional and modified OVD) according to fulfilled statistical assumptions. These two groups were compared for statistically significant difference regarding all parameters that were collected as per section 3.5 of this protocol. These statistical comparisons were made both preoperatively to determine baseline characteristics of the study participants and postoperatively to determine any significant difference between the two groups. Within the same group whether traditional or reduced OVD, all of the aforementioned parameters were compared again pre- and postoperatively this time using either one sample paired t test or Wilcoxon signed-rank test according to fulfilled statistical assumptions. Significance was considered at P value less than 0.05.

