## **3.4 Identification and Recruitment of Participants**

Potential participants will be identified by screening of all medical records from the above hospital regardless of the time of the surgery.

Study investigators will identify study participants individually after screening of medical records.

Since this study is retrospective, initial surgery consent was considered as the participant consent for the study.

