## **3.6 Data collection and analysis**

Data will be collected by study co-investigators with assistance from IT personnel at the respective hospital from patients records that were identified as eligible for the study according to the inclusion criteria above. According to their data, participants will be split into two groups:

1- Traditional OVD group

In this group of patients, the ICL was implanted utilizing both cohesive and dispersive ophthalmic viscosurgical device.

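### The plan does not prevent exclusions from being decided with technique and outcome in view, because ungraded eye-disease criteria may be applied by unmasked investigators after data collection

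*Combined protocol and SAP*

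**What the plan says.** Section 4.2 sets the stage at which data are stored for analysis: "After collection of data from patients records and its subjection to thorough analysis for incompleteness and exclusion criteria". Exclusion criteria and completeness are thus checked on data already collected.

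Section 3.6 describes the filter before collection. Data are taken "from patients records that were identified as eligible for the study according to the inclusion criteria above"; the exclusion criteria are not mentioned there. On who does the work, Section 3.4 states "Study investigators will identify study participants individually after screening of medical records" and Section 3.6 states "Data will be collected by study co-investigators with assistance from IT personnel at the respective hospital".

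Section 3.5 lists what is in the record. It begins "After enrolment, the record of each participant is examined meticulously for completeness of preoperative and postoperative data", and the items include "date of the procedure and its operative notes including laterality and surgical steps" as well as preoperative and postoperative acuity, intraocular pressure and endothelial measurements.

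The Exclusion Criteria require the ocular conditions to have been present preoperatively. Some are named diagnoses. Others carry an undefined grade (unstable refraction, severe ocular surface disease, uncontrolled inflammation), and the list ends with "macular scarring or any other retinal issue that may adversely affect vision after surgery". The primary outcome in Section 3.6 is unaided visual acuity after surgery.

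**The concern.** An exclusion is harmless to a comparison when it depends only on what was known before treatment. It can bias the comparison when the person deciding knows the treatment and the result and the criterion leaves room for judgement. All three elements can occur together here: the technique is in the operative note, the result is in the postoperative visits, and the open retinal criterion concerns vision after surgery, which is what the primary outcome measures. A poor unaided acuity could prompt a closer look for an old retinal or surface problem that would not be sought in an eye that did well.

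If this happened more in one group than in the other, the acuity comparison and the adverse-event comparison would both shift. If it happened equally in both, much of the effect on the between-group difference would cancel, but the adverse-event rates would look better in both groups. Section 2 asks whether the reduced-OVD technique is safe, so that matters as well.

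**Working it through.** The plan states no sample size, standard deviation, effect size or power, so there is no figure of its own to reproduce. The main check is of the order of steps.

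**Sequence**

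1. Section 3.3.1.1 makes both inclusion and exclusion criteria conditions of enrolment.
2. Section 3.4 has investigators screen records and pick participants one at a time.
3. Section 3.5 has the full record examined for completeness after enrolment.
4. Section 3.6 has data collected from records that met the inclusion criteria.
5. Section 4.2 has the collected data checked for completeness and exclusions, then stored.

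Steps 1 and 2 allow exclusions at screening; step 5 has them checked after collection. No section settles which stage governs. Screening does not hide outcomes either: the inclusion criteria ask for at least two postoperative visits within a year, so confirming eligibility means opening the postoperative part of the record. At neither stage does the plan call for masking, a preoperative-only review, a second assessor or a log of exclusions by reason and group.

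**Illustration 1: simple arithmetic (all inputs assumed)**

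Take 100 eyes in one group, 97 with mean logMAR 0.05 and 3 at 0.40.

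- All eyes: (97 × 0.05 + 3 × 0.40)/100 = (4.85 + 1.20)/100 = 0.0605.
- Without the 3 eyes: 0.050. The shift is 0.0105 logMAR, which is small.
- Five eyes with adverse events: 5/100 = 5.0%. Excluding 2 of them: 3/98 = 3.1%, a relative fall of (5.0 − 3.1)/5.0 = 38%.

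**Illustration 2: simulation (all inputs assumed)**

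Unpaired t test, two-sided 0.05 (the plan gives 0.05 without sidedness), normal outcome with SD 1, 10,000 runs. The k worst outcomes are removed from one group only.

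| Per group | k removed | Mean shift (SD) | Rejection rate, no true difference | Power, true harm 0.5 SD in that group |
|---|---|---|---|---|
| 30 | 0 | 0.00 | 0.050 | 0.481 |
| 30 | 1 | 0.07 | 0.062 | 0.385 |
| 30 | 3 | 0.19 | 0.128 | 0.237 |
| 50 | 0 | 0.00 | 0.052 | 0.705 |
| 50 | 2 | 0.09 | 0.080 | 0.558 |
| 50 | 5 | 0.19 | 0.176 | 0.370 |
| 100 | 0 | 0.00 | 0.052 | 0.940 |
| 100 | 4 | 0.09 | 0.108 | 0.838 |
| 100 | 10 | 0.19 | 0.308 | 0.616 |

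As a check, the power formula with nothing removed gives 0.491, 0.705 and 0.942, which agrees with the simulation.

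These are upper-end scenarios, because every exclusion is a worst outcome and all come from one group. They show the direction and how it grows with sample size. They do not measure bias in this study.

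**The case against.** The strongest reply is that the plan already contains the main safeguard. The criteria are listed in advance, every ocular condition must have been present before surgery, and a preoperative baseline visit is required. Cataract, glaucoma, Fuchs' dystrophy and corneal scarring are named diagnoses with little room for relabelling. The retinal wording can be read as a forward-looking preoperative judgement. Sections 3.3.1.1 and 3.4 place eligibility at screening, so the Section 4.2 check may be only a final one. Unmasked eligibility review is also common in retrospective record studies.

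Most of this stands, and it narrows the point to the ungraded and open-ended criteria. It does not close the point. The preoperative limit says when the condition must have existed, not when it must have been recorded or which notes may be used to decide. Nor is the gap inherent in retrospective work, since the ocular criteria can be judged from preoperative notes before outcomes are abstracted.

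A reader might infer more than the documents support:

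- **That poor results were in fact removed, or that every exclusion was made after outcomes were known.** There is no evidence of the first, and the screening text allows some exclusions earlier.
- **That the damage would be beyond repair.** The source is existing hospital records. An eye left out of the data sheet can be re-screened and its outcomes abstracted.
- **That the investigators are judging their own surgery.** Sections 1 and 2 show that the authors name and study the technique; no section says that they operated or that the abstractors were the surgeons.

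**Conclusion.** The point holds as a gap in the plan: outcome-dependent exclusion is not prevented. It rests on the stated order in Section 4.2, the absence of any masking, and the undefined terms in the Exclusion Criteria. It does not rest on any assumed motive. Bias in the between-group comparison needs unequal exclusion of poor results. Its size cannot be estimated from the documents, and the figures above depend wholly on assumed numbers and one-sided removal. This warrants a cheap improvement to the procedure and the reporting; it does not show that the comparison is invalid.

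**What to change.** Amend Sections 3.4 and 4.2 to fix the order of steps.

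1. Apply the age criterion and the ocular exclusions from the preoperative record only. Count a condition only if it was documented at a preoperative visit.
2. Lock that list before technique and outcomes are abstracted.
3. Check the visit-count and completeness criteria afterwards, since these need the postoperative record.
4. Section 3.6 says collection began in March 2024. For records already abstracted, have existing staff repeat the ocular screening from preoperative notes, without reference to group or outcome.
5. Report exclusions by reason and technique group.
6. Add a sensitivity analysis that restores ocular-excluded eyes with available outcomes.

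The cost is a second pass through each record and a screening log; no new data are needed. The downside is that a few eyes with disease first noted after surgery stay in the analysis.

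### Section 4.2 has no rule for sparse categorical tables, so Chi-squared P values for adverse events could mislead if events are few, and no interval is planned to support a safety statement

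*Combined protocol and SAP*

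**What the plan says.** Section 4.2 assigns a single test to categorical data: "Categorical variables were described using frequencies and percentages and were analysed using Chi-squared test". The threshold is also there: "Significance was considered at P value less than 0.05". Numerical data are treated differently. For them "Unpaired t test or Mann-Whitney test was used to compare the two groups", with the choice depending on whether assumptions are met. No matching rule exists for categorical data, and the plan mentions no exact test, continuity correction, expected-count check or confidence interval.

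Section 3.6 lists among the secondary outcomes "the observed adverse events that can happen during the operation or postoperatively", without types, definitions or expected rates. Recorded as occurred or not, these are categorical, so Chi-squared is the only test the plan offers for them.

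Two further passages determine how sparse the tables might be. Section 4.1 sets no target number: "This study involves a convenient non-probability sample based on the availability of patients records". Section 3.3 leaves the group ratio open: "the initial group allocation occurred before the commencement of the study on the basis of surgeon and patient preference".

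**The concern.** The Chi-squared P value is a large-sample approximation that becomes unreliable when expected counts are small. Section 1 credits the lens with a very good safety record, so few events per type is plausible. Section 3.7 removes every participant with any missing item, which can only reduce the groups. The authors already accept, for numerical data, that the test should depend on its assumptions. They do not carry this over to the tables where it may matter most.

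Section 2 asks whether the reduced-OVD technique is safe and suitable, and adverse events carry part of that answer. Two errors are possible. A chance split of a few events could be reported as a significant difference. Or a non-significant P value from very few events could be taken as reassurance although the data exclude little. The plan offers no interval that would show the second.

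**Working it through.** **Inputs.** From section 4.2: Chi-squared test, threshold 0.05. The documents give no group sizes, ratio or event rates, so there is no figure of the plan's to reproduce. Assumed here: the group sizes shown below, and a common true event rate of 0.5% to 5% in both groups.

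**Step 1: a few events, equal groups.** For *a* of *n1* against *b* of *n2*, with *N* = *n1* + *n2* and *m* = *a* + *b*, the uncorrected Pearson statistic is N[a(n2−b) − b(n1−a)]² / [n1·n2·m·(N−m)].

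- 4/50 vs 0/50: 100 × 200² / (50 × 50 × 4 × 96) = 4.167, P = 0.041. The expected number of events is 4 × 50/100 = 2 per group.
- Fisher, two-sided: 2 × (50·49·48·47)/(100·99·98·97) = 2 × 0.0587 = 0.117.
- For 4 vs 0 in equal groups of 20 to 500 each, Chi-squared gives 0.035 to 0.045 and Fisher 0.106 to 0.124.

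Given four events in all, a 4–0 split one way or the other arises by chance about 12% of the time, yet the planned test calls it significant.

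**Step 2: one event against none.** With the event in the group of size *n1*, the statistic reduces to N·n2 / [n1(N−1)], roughly n2/n1. It must exceed 3.84, so the other group must be more than about 3.8 times as large.

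| Group with the event : other group | Statistic | Chi-squared P |
|---|---|---|
| 50:50 | 1.01 | 0.315 |
| 25:75 | 3.03 | 0.082 |
| 21:79 | 3.80 | 0.051 |
| 20:80 | 4.04 | 0.044 |
| 80:20 | 0.25 | 0.62 |

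Fisher for 1/20 vs 0/80 is 20/100 = 0.20. For 2/20 vs 0/80, Chi-squared gives 0.004 and Fisher 0.038.

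**Step 3: type I error.** Sum the product of the two binomial probabilities over all tables with P < 0.05, using the same true rate in both groups. Entries are percentages for the Chi-squared test.

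| Groups | Rate 0.5% | 1% | 2% | 5% |
|---|---|---|---|---|
| 50:50 | 0.02 | 0.19 | 1.30 | 4.34 |
| 33:67 | 0.85 | 2.21 | 3.80 | 3.46 |
| 25:75 | 0.48 | 1.28 | 2.45 | 3.32 |
| 20:80 | 6.51 | 8.77 | 8.74 | 4.71 |
| 25:100 | 7.35 | 9.12 | 8.06 | 4.00 |
| 40:160 | 8.78 | 8.80 | 5.95 | 3.45 |

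The 4:1 excess comes largely from the single-event table. At 20:80 and a 1% rate, exactly one event, in the smaller group, has probability 20 × 0.01 × 0.99^99 = 7.4%, out of the 8.77%. Fisher's type I error was at most 3.2% in every scenario run, and 0.00 to 0.04% at 50:50 with rates of 1-2%.

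**Step 4: what no events would show.** The exact two-sided 95% upper limit for 0/50 is 1 − 0.025^(1/50) = 7.1%.

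**The case against.** The strongest reply is that the harm depends on data nobody has described. The documents do not say that adverse events are rare. Preference-based allocation does not imply a 4:1 ratio, and screening all records whatever the surgery date (section 3.4) does not imply small groups. The computed type I error was below 5% at 1:1, 2:1 and 3:1, and even at 20:80 it falls to 4.71% when the rate is 5%. The outcome is secondary, biostatisticians were consulted (section 4), and Fisher's test rejects even less often than Chi-squared, so it cannot cure low power.

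Most of this stands, and it limits the point. A reader might infer that the safety P values are bound to be wrong, that unequal groups in general produce false signals, or that one event would be declared significant. The documents support none of these. The single-event result needs a ratio above about 3.8:1 with the event in the smaller group, and it is already lost at 21:79. Nor is Chi-squared unsuitable throughout: for well-filled tables, such as gender is likely to give, it is adequate. Nor does any section say that non-significance will be read as safety.

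The reply does not remove the gap itself. The plan has no rule for sparse tables. Equal groups do not avoid the problem, since a 4–0 split there is significant by one test and not by the other. The remark about Fisher's low power is a reason to add intervals, not a reason to leave the section as it is.

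**Conclusion.** The point holds as a conditional weakness worth correcting. The omission can be read directly from section 4.2. Its effect depends on unstated quantities. If events are few, the Chi-squared P value can be about a third of the exact one (0.041 against 0.117 for 4/50 vs 0/50). If the groups are also about 4:1, the nominal 5% error can reach 8-9% (20:80 and 25:100, rates of 1-2%; 5.95% at 40:160 with a 2% rate). In the 1:1 to 3:1 scenarios computed it stays below 5%, and one event is not significant.

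For the safety aim, the missing intervals matter more than the choice of test. Under the assumed 50 per group, no events at all would still be compatible with a true rate of up to 7.1%.

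**What to change.** In section 4.2, after the sentence on categorical variables, add:

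> For any 2×2 table with an expected count below 5, including each adverse event, Fisher's exact test will be used. Each group's adverse-event rate will be reported with an exact (Clopper-Pearson) 95% CI, and the risk difference with a 95% CI. The safety conclusion will rest on these intervals, and a non-significant P value will not be taken as evidence of safety.

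The method for the risk-difference interval should be named, since a simple normal-approximation interval has the same weakness with small counts.

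The cost is wording and a few extra table columns. No new data are needed, and Fisher's test is available in SPSS, the package the section names. The downside is that Fisher's test is conservative and rejects less often than Chi-squared, so a real difference is less likely to reach significance. That is why the intervals, not the P value, should carry the safety statement.
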